1.1 Trial background and rationale

Empagliflozin (Jardiance™) is one of several SGLT-2 inhibitors commercially available and licensed in the UK as a treatment for Type 2 diabetes. All of the SGLT-2 inhibitors have been shown to lower HbA1c and result in weight loss. However, observed weight loss is less than predicted for these agents, and the underlying mechanisms for this are unknown.

It is hypothesised that appetite hormones may play a role in this weight loss deficit. Those likely to be involved are peptide Y-Y (PYY) and ghrelin, as both are important in the control of appetite and weight regulation. They are secreted from intestinal L cells which are found in the distal small intestine. Ghrelin, which stimulates hunger, has been shown to increase with weight loss and energy restriction diets ¹. Glucagon-like peptide 1 (GLP-1) is another hormone which is involved in the regulation of appetite and satiety along with other glucose homeostatic effects ². There are no studies that have investigated the impact of SGLT-2 inhibitors on appetite hormones and effect on body composition. It is essential to understand these mechanisms in order to maximize the weight loss achievable with these agents. They may need to be combined with appropriate dietary measures such as energy restriction diets and weight-lowering or weight-neutral hypoglycaemic therapies for optimal clinical benefit.

The aim of the study is to explore the relationship between appetite hormones and Empagliflozin (Jardiance™) in order to understand the underlying mechanisms for observed weight loss which does not equate with that predicted for these agents.

1.2 Trial objectives/hypotheses

- The primary objective is to investigate the cause for the discrepancy in predicted and observed weight loss with Empagliflozin (Jardiance™) by measuring PYY, as a marker of appetite regulation.
- The secondary objectives are to determine the effects of Empagliflozin (Jardiance™) on other markers of appetite regulation, resting energy expenditure, total body weight and body composition.

2 Methods

2.1 Trial design

The trial is a randomised, double-blind placebo-controlled 4 arm parallel trial, in which participants are randomised (1:1:1:1) to one of the four arms at baseline: Empagliflozin 25mg once daily; Placebo only; Empagliflozin 25mg once daily plus energy restriction diet; Placebo once daily plus energy restriction diet. Participants are followed up for 24 weeks, with intermediate assessments after 2 weeks, 6 weeks and 12 weeks.

2.2 Randomisation

Randomisation is stratified for age [1. \leq 50years 2.>50years] and body mass index (BMI; [1. BMI 25.0-29.9kg/m2 2. BMI \geq 30.0kg/m2]).

2.3 Sample size

The power calculation is based on the primary outcome of total PYY with a standard deviation of area under the curve (AUC) of 96.2pg/ml, based on a study looking at the influence of resistance and aerobic exercise on hunger and circulating levels of total PYY in healthy males³. To detect a minimum clinically significant difference of 120pg/ml in AUC of total PYY between groups, we will require 15 patients (60 in total) in each of the four arms to complete the trial with 80% power and 2-sided alpha of 1.7%. This will allow three comparisons between arms.

2.4 Framework

This is a 4 arm parallel trial with two interventions (Empagliflozin and an energy restriction diet). There will be three co-primary analyses: 1) Empagliflozin only versus placebo control, 2) energy restricted diet only versus placebo control, and 3) Empagliflozin & energy restricted diet vs placebo control.

2.5 Interim analyses and stopping guidance

None

2.6 Timing of final analysis

Analyses described in this SAP will be performed following completion of the trial and database lock.

2.7 Timing of outcome assessments

Outcomes are assessed at 24 weeks, with intermediate assessments at 2 weeks, 6 weeks and 12 weeks.

2.8 Blinding

This is a double-blind study. The treatment that is double-blinded is Empagliflozin. Both participants and study investigators are blinded to Empagliflozin allocation by way of a placebo medication that is identical in appearance to Empagliflozin. All measurements, including the primary outcome, are recorded with blinding to treatment allocation in place. Diet allocation is not blinded because it is not possible to blind this. The statistician performing the analyses will not be blinded. This is because the statistician needs to be able to identify the placebo group to know which of the four arms is the reference group for the three primary comparisons with placebo.

3 Statistical principles

3.1 Adherence

Adherence to randomised treatment was assessed at every study visit and documented in the CRFs. Adherence to Empagliflozin/placebo was checked by the study nurse counting in tablets that had not been taken. Participants are deemed to be compliant if they had taken 80% or more of their randomised medication.

Adherence to the energy restriction diet was assessed at visits 2-4 by checking the food diary. Participants are deemed to be compliant if they met their individual diet energy intake restriction threshold.

3.2 Analysis populations

3.2.1 Complete Case Population

All tests of the effect of treatment on outcomes will be conducted on a complete case (CC) population, using intention to treat principles. Patients will be excluded from analyses if they have missing data on any of the variables required for the analysis in question. Those with missing data at baseline will be included in the analysis using the missing indicator method. Detail is given in section 5.3.2. This population will be used for the main analysis of the primary outcome as well as all analyses of secondary outcomes.

3.2.2 Full analysis data set using multiple imputation for missing data

A sensitivity analysis using multiple imputation will be used to impute missing data, to assess the robustness of the conclusions to missing data. More detail is in section 5.3.2. This population will be used for sensitivity analyses of the primary outcome. It will not be used for secondary outcomes.

3.2.3 Per-protocol Population

The per protocol (PP) population are those who were compliant with the protocol and have complete data for the analysis concerned on a 'by analysis' basis. The PP population will be defined as follows for each arm:

- Empagliflozin 25mg once daily: Participants must take at least 80% of the prescribed treatment for the duration of the study.
- Placebo only: Participants must take at least 80% of the prescribed (placebo)
 treatment for the duration of the study, and not be prescribed Empagliflozin by their
 GP. This will be determined by the concomitant medications recorded for each
 patient at each visit.
- Empagliflozin 25mg once daily plus energy restriction diet: Participants must take at least 80% of the prescribed treatment for the duration of the study, and meet their individual diet energy intake restriction threshold, following food diary checks, at visits 2-4.
- Placebo once daily plus energy restriction diet: Participants must take at least 80% of the prescribed (placebo) treatment for the duration of the study, not be prescribed Empagliflozin by their GP, and meet their individual diet energy intake restriction threshold, following food diary checks, at visits 2-4.

Participants with a substantial protocol deviation logged, which in the opinion of the investigators might affect the primary outcome, will also be removed from the PP analysis. This population will be used for sensitivity analyses of the primary outcome. It will not be used for secondary outcomes.

4 Trial population

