8.10 Discontinuation/Withdrawal of Participants from Study Treatment

Each participant has the right to withdraw from the study at any time without needing to give a reason. In addition, the Investigator may discontinue a participant from the study at any time if the Investigator considers it necessary for any reason including:-

- Participant intolerance to study medication, as assessed at each visit by the study team, will necessitate withdrawal of participant from the study as study drug dose will not be reduced during the trial
- Ineligibility (either arising during the study or retrospective having been overlooked at screening)
- Significant protocol deviation
- Significant non-compliance with treatment regimen or study requirements
- An adverse event which requires discontinuation of the study medication or results in inability to continue to comply with study procedures
- Disease progression which requires discontinuation of the study medication or results in inability to continue to comply with study procedures
- Consent withdrawn
- Lost to follow up

The reason for withdrawal will be recorded in the CRF and medical records if known. If the participant is withdrawn due to an adverse event, the investigator will arrange for safety follow-up visits or telephone calls until the adverse event has resolved or stabilised. The duration of safety follow-ups will be at least five half-lives of the study medication. The half-life of Empagliflozin (Jardiance™) is 12.4 hours, thus the duration of safety follow-ups will be rounded up to be at least 72 hours (or 3 days).

The participant will be withdrawn from the study if they lose capacity and data collected up to that point will be used for analysis. As analysis will be on an intention-to-treat basis, there will be analysis of all data of participants receiving study medication (e.g. most safety analyses) and data will be admitted to the database even after the participant has withdrawn from the study.

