Certain circumstances will necessitate the stopping or interruption of the study medication for a particular participant. Adverse event review and other safety/acceptability assessments will provide the information for the study clinician to withdraw or interrupt the study drug at any time during the trial. Specifically, it may be necessary to interrupt treatment with SGLT2-ingibitors (such as Empagliflozin (Jardiance™)) in participants who are hospitalised for major surgery or acute serious illness; treatment may be restarted once the participant's condition has stabilised and only once the necessary safety assessments have been performed. The decision to stop or interrupt and subsequently re-start the study treatment Empagliflozin (Jardiance™) will be documented in the participant's medical notes.

Any decisions regarding the withdrawal of participants from the study will be made by the study clinician and Principal Investigator.

Each participant will have a copy of the consent form and patient information leaflet placed in their hospital medical records. This will also include explicit notice of their in-study medication and a standard label will be used on the front of the medical notes to highlight to any reviewer that this individual is taking part in the study and any issue regarding contra-indication of a procedure or medication outside of the study should be discussed with a study clinician.

The standard label template is provided by the local trust and should contain the following information:

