9. TREATMENT OF TRIAL PARTICIPANTS

9.1 Description of Study Treatment & Pharmacy Process

The study medication is Empagliflozin (Jardiance[™]) which is an oral film-coated tablet manufactured by Boehringer Ingelheim pharmaceutical company. Placebo will also be manufactured and supplied by Boehringer Ingelheim. Both Empagliflozin (Jardiance[™]) and the placebo can be described as follows: pale yellow, biconvex film-coated tablets, one side debossed with the Boehringer Ingelheim company symbol and the other side debossed with "S25". The dosage will be 25mg once daily for Empagliflozin (Jardiance[™]), which is the maximum dose, licensed for the treatment of Type 2 Diabetes in the UK. The placebo will be labelled as '25mg once daily' to match. There is a lower dose of Empagliflozin (Jardiance[™]) 10mg daily. However, this dose will not be used in the study and participants who do not tolerate Empagliflozin (Jardiance[™]) 25mg daily will be discontinued from the study.

The ingredients of the placebo are:

- > Tablet core
- Lactose monohydrate
- Microcrystalline cellulose
- Hydroxypropylcellulose
- Croscarmellose sodium
- Colloidal anhydrous silica
- Magnesium stearate
- > Film coating
- Hypromellose
- Titanium dioxide (E171)
- Talc
- Macrogol (400)
- Iron oxide yellow (E172)

The licensed product Empagliflozin (Jardiance™) will be handled according to UHL pharmacy in-house protocols. Specifically, the employment, dosing, handling, storage and destruction of Empagliflozin (Jardiance™) and its placebo will be conducted in accordance with the specified conditions of its approved labelling and in line with our UHL pharmacy guidelines. All study medication dosage will not exceed the stated recommendations of local guidelines and the British National Formulary. All contra-indications will be checked as part of the eligibility criteria.

Boehringer Ingelheim will supply both Empagliflozin (Jardiance™) and the placebo to the third party company ALMAC who will arrange the packaging, blinding and labelling of both Empagliflozin (Jardiance™) and the placebo prior to delivery and storage of the finished blinded stock to Leicester General Hospital Pharmacy.

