11.7 Inclusion in Analysis

All analyses of outcome data will be carried out on a complete case basis according to randomised group. Therefore those with missing outcome data will be excluded from this analysis. As a sensitivity analysis, for the primary and main secondary outcome, multiple imputation will be used to perform an intention to treat analysis, and to assess the impact of missing outcome data. We will also conduct a per protocol analysis excluding those who report no longer taking their randomised treatment at the four follow ups.

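### The SAP's per-protocol rule (80% of tablets over the study) drops the protocol's condition that participants are still on randomised treatment at the follow-ups, including week 24

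*SAP*

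**What the plan says.** The protocol describes the per-protocol analysis twice. Section 11.1 restricts it to participants who stay on their regimen throughout the study. Section 11.7 describes it as "excluding those who report no longer taking their randomised treatment at the four follow ups". The four follow-ups are weeks 2, 6, 12 and 24.

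The SAP uses a different rule. Section 3.1 states: "Participants are deemed to be compliant if they had taken 80% or more of their randomised medication". It describes the measurement as follows: "Adherence to Empagliflozin/placebo was checked by the study nurse counting in tablets that had not been taken". Section 3.2.3 applies the threshold in each arm; for empagliflozin alone the wording is "Participants must take at least 80% of the prescribed treatment for the duration of the study". The placebo arms add that the GP must not have prescribed empagliflozin, and the diet arms add the food-diary threshold at visits 2 to 4. Section 3.2.3 also removes participants with a logged deviation that the investigators consider substantial and liable to affect the primary outcome. Nothing in 3.1 or 3.2.3 concerns when the missed doses fall or whether the participant is taking tablets at visit 5.

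SAP 5.1 defines the primary outcome as the change in time-averaged PYY AUC from baseline to week 24. SAP 3.2.3 and 5.4.4 use the per-protocol set only for a sensitivity analysis of that outcome.

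**The concern.** The endpoint comes from blood samples taken at one visit, whereas the adherence rule is a total over the whole study. A total of 80% can be reached by someone who misses a dose now and then and is on drug at week 24, or by someone who takes every tablet for months and then stops. The SAP treats these two people alike. The protocol would keep the first and exclude the second.

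The documents foresee people who are off drug but still in the study. Protocol 8.10 says that "it may be necessary to interrupt treatment with SGLT2-ingibitors" in participants admitted for major surgery or acute serious illness, with restart only after the condition is stable and safety checks are done. Protocol 9.1 separates suspending the drug from withdrawing the participant, and protocol 9.3 makes withdrawal for poor compliance discretionary.

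The per-protocol set supports the plan's only adherence-restricted analysis. If its empagliflozin arms include people who are unexposed at the endpoint, a null result could mean no PYY effect on drug, or an effect that had gone after stopping.

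**Working it through.** **Inputs**
- Duration (SAP 2.1): "Participants are followed up for 24 weeks", so 24 × 7 = 168 days.
- Dosing frequency (protocol 9.1): "The dosage will be 25mg once daily for Empagliflozin", so one tablet a day and 168 tablets.
- Threshold (SAP 3.1 and 3.2.3): at least 80%.
- Visit 5 window (protocol 6.1): ±5 days, so 163 to 173 days.
- Half-life (protocol 8.10): "The half-life of Empagliflozin (Jardiance™) is 12.4 hours".
- Planned completers and difference (SAP 2.3): 15 per arm, 120 pg/ml.

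**The protocol's own figure.** 5 × 12.4 h = 62 h, which protocol 8.10 rounds up to at least 72 h. The figure reproduces. The protocol gives it as a minimum safety follow-up.

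**Longest run off drug that still passes, whole-study reading.** Days off = days − (0.80 × days, rounded up).
- 168 days: 0.80 × 168 = 134.4, so 135 tablets are needed and 168 − 135 = 33 days off. Check: 135/168 = 80.4% passes and 134/168 = 79.8% fails.
- 163 days: 130.4, so 131 tablets are needed and 32 days off.
- 173 days: 138.4, so 139 tablets are needed and 34 days off.

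**Per-interval reading.** SAP 3.1 says that adherence was assessed at every visit but does not say whether the 80% applies to each interval. If it does, the last interval (weeks 12 to 24) has 84 days: 0.80 × 84 = 67.2, so 68 tablets are needed and 84 − 68 = 16 days off.

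**Plasma exposure.** 33 × 24 / 12.4 = 63.9 half-lives; 16 × 24 / 12.4 = 31.0 half-lives. On either reading, plasma exposure at visit 5 is negligible. This says nothing about how quickly PYY changes after stopping.

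**Dilution, if the effect has fully reverted (assumption).** With k such people among n in an empagliflozin arm, the drug contrast is multiplied by (1 − k/n). With n = 15:
- k = 1: 1/15 = 6.7%, and 120 × 14/15 = 112 pg/ml.
- k = 2: 2/15 = 13.3%, and 120 × 13/15 = 104 pg/ml.

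In the combined arm only the drug's part of the effect would be diluted, because the diet may continue. A per-protocol arm smaller than 15 makes each person's share larger.

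**The two rules side by side**, for a participant who takes every tablet for 135 days, stops, says so at visit 5 and gives the samples:
- Protocol 11.1: not on the regimen throughout, so excluded.
- Protocol 11.7: reports no longer taking treatment at a follow-up, so excluded.
- SAP 3.2.3: 80.4% taken, so included unless the investigators judge otherwise under the deviation clause.

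**The case against.** The other side has several fair arguments.

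- **The opening sentence of SAP 3.2.3** limits the set to people who complied with the protocol, and the 80% rule is itself tied to the length of the study. Someone who stopped for good could be read as outside the set. However, the section then defines compliance arm by arm through the 80% rule, and SAP 3.1 calls anyone at 80% compliant. The text does not force the stricter reading.
- **Other routes remove late stoppers.** Protocol 8.10 and 9.1 require withdrawal for intolerance, and 9.5 does so when an excluded medication is needed. These routes narrow the gap. They do not cover voluntary late stopping, or an interruption not restarted before visit 5.
- **The deviation clause** might catch such cases. A reader might infer that a permitted interruption can never count as a substantial deviation. Neither document says so, and the SAP does not define the term. What stands is that the exclusion rests on judgement and is not automatic.
- **Protocol 11.7 is loosely worded** and could mean off treatment at all four follow-ups. Section 11.1 points to the stricter reading.
- **The half-life comparison is easily overstated.** A reader might divide 33 days by the 72 h figure and say that the rule allows 11 times the protocol's washout. The documents do not support that label, because 72 h is a minimum safety follow-up. The protocol mentions wash-out only for the telephone call about one week after the last dose, and 33/7 = 4.7.
- **Reversion of PYY is not established.** Protocol section 4 presents the appetite response as an adaptation, and neither document gives its course after stopping.

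**Conclusion.** The inconsistency is real. SAP 3.2.3 omits a condition that protocol 11.1 and 11.7 both contain, and gives no reason. A participant who is off randomised tablets at week 24 can be per protocol under the SAP and excluded under the protocol.

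The bound of 33 days (32 to 34 over the visit window), or 16 days per interval, is a worst case. It requires full adherence up to stopping and then no doses at all. The documents do not show how many participants would be affected. The loss of about 6.7% per person assumes 15 per arm and full reversion of PYY. Without reversion there is no dilution, though the two definitions still disagree.

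The reach is limited. The main complete-case analysis and all secondary outcomes are unchanged, and the documents tie no decision to the per-protocol result. A reader might infer that the primary conclusion is at risk, or that the per-protocol result is certainly biased towards zero; the documents support neither. The definition should still be corrected, because the change is small and this is the plan's only check on the effect in adherent participants.

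**What to change.** In SAP 3.2.3, keep the 80% rule and add one condition for all four arms: participants recorded at visit 5 as no longer taking their randomised tablets, active or placebo, are excluded from the per-protocol set. Applying it to placebo tablets as well keeps the arms comparable. State also whether the 80% applies to the whole study or to each visit interval.

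The source is the compliance assessment and drug accountability already planned for visit 5 in protocol 8.8. A returned-tablet count shows how many doses were missed but not when, so reported status at the visit is the operative item. If a last-dose date is available, the sponsor may pre-specify a window before analysis. Protocol 11.7 sets no such window and no particular cut-off is required. SAP 3.1 is written in the past tense, so a new CRF item may no longer be feasible, and the fix does not depend on one.

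The cost is a sentence or two in the SAP. The downside is that the per-protocol set may lose a few participants. The primary analysis stays as it is.

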8.5 Investigations

Primary Outcome Measurement

Appetite Hormones (visits 1, 2, 3, 4, 5) - Ghrelin, PYY, GLP-1

The primary outcome is change in appetite hormones from baseline to week 24 and between groups.

For this, participants are required to fast for 10 hours before study visits 1-5, and prior to the measurement of appetite hormones at each visit, there will be dietary standardisation. Specifically, there will be a 48 hour standardisation plan incorporating a 24 hour meal standardisation plan, and on the day of their study visit a standardised breakfast. The standardisation plans are described below:

> 48 Hour pre-visit Standardisation

For the 48 hours before study visits 1-5, participants will be asked to refrain from:

- completing any structured form of physical activity,
- consuming alcohol
- consuming caffeine

Participants will be issued with food and drink diaries (see Section 8.7, pg. 26) at the familiarisation visit (visit 0) within which to record their intake and this will be reviewed at each visit to ensure that they are adhering to the 48 hour restriction period. Participants will be asked whether or not they have completed any structured form of physical activity at each visit.

24 Hour Meal Standardisation

In addition to the 48 hour pre-visit standardisation described above, for the 24 hours before study visit 1-5, participants will be asked to:

- standardise their food and drink intake (i.e., to consume the same food and drinks before each study visit)
- consume the standardised evening meal provided to them at least 10 hours before their visit. This
 will be based on their energy requirements**. A set meal will be provided dependent on whether
 their energy requirement is above or below a 1500 Kcal threshold.
- continue to fast until their visit (they will be provided with a standardised breakfast at their visit)

Participants will be issued with food and drink diaries (see Section 8.7, pg. 26) at the familiarisation visit (visit 0) within which to record their intake and this will be reviewed at each visit to ensure that they are adhering to the 24 hour meal standardisation period.

**participants daily energy requirement will be estimated at their familiarisation visit (visit 0) using the Mifflin St Jeor Equation (MSJE).

Breakfast Standardisation

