8.8 Subsequent Assessments

Table 1 (pg. 27) shows the visit numbers and window periods for the visits. A detailed description of each assessment is provided in Section 8 – Study Procedures (pg. 21).

Visit 0 (Screening Visit) – clinic visit (- 1 week to - 2 days)

During this visit, there will be an eligibility check of inclusion/exclusion criteria, concomitant medications recorded and a safety assessment including physical examination performed. Screening blood tests will be performed if not checked in the last 3 months. Participants will be provided with a diary within which to record their consumption of food and drink throughout the course of the study. Specifically, participants will be asked to record all food and drink consumed, including details about the amount/portion size consumed, a description of what was consumed (i.e., the brand) and the time that it was consumed for a minimum of four days to include the 48 hour restriction period. The diaries will be used to determine whether or not participants have adhered to the 48 hour pre-visit restriction period (see Section 8.4. pg. 22) and their daily energy restriction diet prescription (if applicable; see Section 8.5, pg. 25). The diaries will be checked by a member of the research team at each visit.

Visit 1 (Baseline Visit, 0 weeks) – clinic visit Dispensing Visit

During this visit, there will be a check for ongoing consent to participate in the trial, record of concomitant medications and baseline blood tests performed including renal and liver function tests for safety. Study drugs will be dispensed following randomization. Energy restriction diet will be prescribed if participants are randomized to this intervention.

Visit 2 – clinic visit at 2 weeks (- 5 days to + 5 days)

Dispensing Visit

During this visit, there will be a check for ongoing consent to participate in the trial, record of concomitant medications and blood tests performed for safety including renal and liver function tests. There will be assessment of study drug compliance and/or energy restriction diet compliance. Drug accountability will be performed.

Visit 3 – clinic visit at 6 weeks (- 5 days to + 5 days)

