During this visit, there will be a check for ongoing consent to participate in the trial, record of concomitant medications and blood tests performed for safety including renal and liver function tests. There will be assessment of study drug compliance and/or energy restriction diet compliance. Drug accountability will be performed.

Visit 4 – clinic visit at 12 weeks (- 5 days to + 5 days)

Dispensing Visit

During this visit, there will be a check for ongoing consent to participate in the trial, record of concomitant medications and blood tests performed for safety including renal and liver function tests. Study drugs will be dispensed again at this visit. There will be assessment of study drug and/or energy restriction diet compliance. Drug accountability will be performed.

Visit 5 (Final Visit) – clinic visit at 24 weeks (- 5 days to + 5 days)

During this visit, there will be a check for ongoing consent to participate in the trial, record of concomitant medications and blood tests performed for safety including renal and liver function tests. There will be assessment of compliance with study drugs and/or energy restriction diet. Drug accountability will be performed.

Telephone Consultation – 7 days after medication discontinuation (- 3 days to + 3 days)

Participants will be contacted by telephone within 3-7 days after study medication discontinuation in order to capture of any potential Adverse Events.

Table 1 – Measures at each Study Visit

Procedure or assessment during experimental period	Visit 0 (Familiarisation Visit) -1 week to – 2 days	Visit 1 (Baseline) 0 weeks	Visit 2 (2 weeks) - 5 days to + 5 days	Visit 3 (6 weeks) - 5 days to + 5 days	4 th Visit (12 weeks) -5 days to +5 days	5 th and Final Visit (24 weeks) - 5 days to + 5 days	Follow-up Telephone Call (1 week after medication completion) - 3 days to + 3 days
Inclusion/Exclusion criteria Explanation of Study Procedures Informed consent	х						
Confirmation of continued will to participate in the study		Х	Х	Х	Х	Х	
Randomisation		Х					
Demographics	Х						
Smoking status and alcohol intake	х						
Medical history Physical examination	Х					Х	
Concomitant Medication review	х	Х	Х	Х	Х	Х	
Height, weight, waist and hip circumference Resting heart rate and blood pressure	х	Х	Х	Х	х	Х	
Dispensing of Study Drug		Х	Х		х		
Study drug accountability			Х	Х	х	Х	

Physical activity questionnaire (IPAQ)		Х	Х	Х	Х	Х	
Appetite questionnaires (VAS, 3-Factor Eating)		Х	Х	х	Х	Х	

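### The SAP's per-protocol rule checks diet adherence only to week 12, although the primary endpoint is at week 24 and the protocol schedules a diet check there

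*SAP*

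**What the plan says.** SAP 3.1 opens with a general statement: "Adherence to randomised treatment was assessed at every study visit and documented in the CRFs". For the diet it then narrows this: "Adherence to the energy restriction diet was assessed at visits 2-4 by checking the food diary". SAP 3.2.3 builds the same limit into the per-protocol definition. In the empagliflozin-plus-diet and placebo-plus-diet arms, participants must "meet their individual diet energy intake restriction threshold, following food diary checks, at visits 2-4". The tablet criterion has no such limit: "Participants must take at least 80% of the prescribed treatment for the duration of the study". A closing clause applies to all arms: "Participants with a substantial protocol deviation logged, which in the opinion of the investigators might affect the primary outcome, will also be removed" from the per-protocol analysis.

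The protocol is wider on diet:

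- Section 8.6 intends the energy restriction to be kept up for the whole study.
- Section 8.8 has the food diaries checked by the research team at every visit and says of visit 5: "There will be assessment of compliance with study drugs and/or energy restriction diet".
- The diet-compliance row of Table 1 carries five marks, which fits visits 1 to 5.
- Section 11.1 restricts the per-protocol analysis to people who stay on their regimen for the whole study, and section 11.7 judges this over four follow-ups, that is, visits 2 to 5.

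**The concern.** A per-protocol analysis of a week-24 outcome is meant to describe people who were following their allocated regimen up to that outcome. Under the SAP's wording, someone in a diet arm can pass the diary checks at weeks 2, 6 and 12, give up the diet, and still satisfy the stated diet criterion when PYY is measured at week 24. The SAP gives no reason for leaving out visit 5, and the omission is narrower than the protocol's own definition.

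The contrasts at stake are diet alone versus placebo and empagliflozin plus diet versus placebo, two of the three co-primary comparisons in SAP 2.4. If the per-protocol result agrees with the main result, a reader will take this as reassurance about non-adherence. That reassurance is weaker than it looks if adherence to one of the two interventions was last checked halfway through.

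**Working it through.** **1. Coverage of the rule.** Visit timing is from protocol 6.1 and 8.3, and the endpoint from SAP 5.1.

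- Visits 2, 3, 4 and 5 are at weeks 2, 6, 12 and 24, each ±5 days.
- The diet rule uses 3 of these 4 post-randomisation visits.
- Nominal interval after the last diet check: 24 − 12 = 12 weeks, and 12/24 = 50% of follow-up.
- With the windows, visit 4 falls on days 79 to 89 and visit 5 on days 163 to 173. The interval is therefore 163 − 89 = 74 to 173 − 79 = 94 days.

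**2. The two documents side by side.**

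| Item | SAP | Protocol |
|---|---|---|
| Diet check at visit 5 | Not named (3.1, 3.2.3) | Scheduled (8.8, Table 1) |
| Span of the per-protocol diet condition | Visits 2 to 4 | Whole study (11.1); four follow-ups (11.7) |
| Span of the per-protocol drug condition | Whole study | Whole study (11.1); four follow-ups (11.7) |

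The SAP is also uneven within itself: SAP 3.1 claims assessment at every visit and then stops at visit 4 for diet. In addition, protocol 8.6 has the energy target reassessed at visit 4, so adherence to the target set then can be seen only at visit 5.

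**3. The plan's sample size, reproduced first.** Inputs from protocol 11.2: difference 120 pg/ml, SD 96.2 pg/ml, two-sided alpha 1.7%, power 80%, dropout 20%.

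- Two-sample t test, noncentrality = δ / (SD × √(1/n₁ + 1/n₂)). With 15 per arm this is 120 / (96.2 × √(2/15)) = 3.42 on 28 degrees of freedom, and power is 80.3%. With 14 per arm power is 76.8%, so 15 is reproduced.
- 15 / (1 − 0.20) = 18.75, rounded up to 19; 4 × 19 = 76. Reproduced.
- None of these figures changes if the per-protocol rule is changed.

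**4. Possible size of the dilution (illustration).** The documents give no rate of stopping the diet late. Assume that k of 15 completers in a diet arm stop after visit 4, that their week-24 effect falls to zero, that they otherwise resemble the rest, and that the SD stays at 96.2. Keeping them gives an expected difference of 120 × (1 − k/15). Excluding them leaves 120 pg/ml with 15 − k against 15.

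| k | Difference if kept (pg/ml) | Power if kept | Power if excluded |
|---|---|---|---|
| 1 | 112 | 74% | 79% |
| 2 | 104 | 66% | 77% |
| 3 | 96 | 58% | 74% |
| 4 | 88 | 50% | 71% |
| 5 | 80 | 41% | 68% |

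For k = 3, the noncentrality if kept is 96 / (96.2 × √(2/15)) = 2.73. If excluded it is 120 / (96.2 × √(1/15 + 1/12)) = 3.22. Under these assumptions the smaller set loses less power than the dilution does. The calculation fits diet alone versus placebo best. In the combined arm only the diet's share of the effect would be lost, so the dilution would be smaller.

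**The case against.** **Other routes out of the set.** SAP 3.2.3 begins by requiring compliance with the protocol and ends with the clause on logged substantial deviations. Protocol 8.10 also allows a participant to be discontinued for significant non-compliance, and without week-24 data that person is not in the per-protocol set. So one cannot infer that every late stopper is retained. These routes are discretionary, however, and the deviation clause works only if a deviation was logged. They narrow the gap without closing it.

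**Only a sensitivity analysis.** This stands. The per-protocol set is used for the primary outcome alone and for no secondary outcome. The main analysis is complete case by randomised group.

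**Direction of bias.** A reader might infer that the rule necessarily pulls the diet contrasts towards no effect. The documents do not support certainty. Late stoppers select themselves, and the protocol describes PYY as appetite-inhibiting, so adherence at week 24 may itself depend on the outcome. Conditioning on it in the diet arms only, against a placebo-only arm with no diet criterion, can introduce a bias of its own. This stands, and it is a real cost of the fix.

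**What a visit 5 check can show.** The diary need be kept only "for a minimum of four days to include the 48 hour restriction period". A visit 5 check may therefore show adherence near the endpoint rather than across weeks 12 to 24. This also stands.

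**The diary itself.** A reader might go further and treat up to half of the minimum four diary days as uninformative because they fall in the 48-hour pre-visit window. Protocol 8.5 does not support this. The 48-hour rule bars structured exercise, alcohol and caffeine. Only the final 24 hours standardise intake, when participants are asked "to consume the same food and drinks before each study visit" and eat a supplied evening meal. Four days is also a minimum. At most the last 24 hours is a weak guide to free-living adherence, which does not justify discarding the whole window.

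**Conclusion.** The inconsistency is real. The SAP's explicit diet criterion ends at week 12, leaves out a check that the protocol schedules at the endpoint visit, and is narrower than the per-protocol definition in protocol 11.1 and 11.7. The per-protocol analysis of two of the three co-primary contrasts can therefore include people who are off the diet at week 24.

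Dilution of the diet effect is the probable consequence. Its size is unknown: the 96 pg/ml at k = 3 depends on an assumed stopping rate and on complete loss of effect, and the direction is not guaranteed. No sample size, alpha or primary conclusion depends on the point. It should be corrected because the SAP and protocol disagree and the correction is small.

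**What to change.** In SAP 3.1 and 3.2.3, replace visits 2 to 4 with visits 2 to 5 for both diet arms, using the visit 5 diary check in protocol 8.8 and Table 1. State which energy target the visit 5 diary is compared with, since protocol 8.6 has the target reassessed at visits 3 and 4. If visit 5 is left out on purpose, say why, and report the departure from protocol 11.1 and 11.7.

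The cost is mainly wording. SAP 3.1 is written in the past tense and leaves unclear whether a visit 5 judgement against the threshold was recorded. If it was not, it would have to be derived from the visit 5 diaries. The per-protocol set will be somewhat smaller, and there will be further post-randomisation selection in the diet arms, which the report should acknowledge when interpreting this analysis.
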